### **13.5 Experimental Period**

Prior to sampling, the subjects will be questioned regarding adherence to the protocol. Female subjects must have a negative urine pregnancy test documented before treatment with test materials.

Subjects will don a disposable undergarment and be examined physically to ensure no evidence of injury, dermatosis, or dermatitis is present at the test sites (Section 15.2). On the abdomen, a sterile surgical marker will be used to demarcate bilaterally 5" x 5" areas of skin to the right and left side of the navel that appear to be similar in condition. On the groin, a sterile surgical marker will be used to demarcate bilaterally 1.5" x 5" areas of skin that appear to be similar in condition.

Prior to collection of the baseline, 30-second, 10-minute, and 6-hour post-prep samples, the skin in each test area will be evaluated for indications of skin irritation, based on the Skin Irritation Scoring System (Section 15.2).

Subjects will be sampled for baseline microbial population on sites randomly assigned on the skin of the abdomen and groin on both sides (Appendix 2). The Cylinder Sampling (Scrub Cup) Technique (Section 13.6) will be used for this and for the post-treatment samples.

The randomly assigned test product, positive control, and negative control will be applied to the test sites per directions presented in Appendix 1. A total of three post treatment sample collections will be performed at each test site for all test materials. All subjects will have samples collected within 30 seconds  $\pm$  5 seconds, 10 minutes  $\pm$  30 seconds and 6 hours  $\pm$  30 minutes post application from both anatomical treatment sites. Following the 10-minute sample being obtained the remaining sample sites will be covered with sterile synthetic-blend gauze sponges and semi-occlusive catheter dressings. Subjects will return 6 hours following product application to be sampled. During product applications, subjects will wear disposable gloves to guard against contamination of the test sites.

If the semi-occlusive catheter dressing has lifted from a test site such that the gauze sponge is no longer secured, the test site will be sampled and the occurrence noted.

Following completion of the final post-product application sampling of a test site, the remaining test material will be wiped/cleansed from the test site with a mild soap and/or tap water.

### **13.6 Cylinder Sampling (Scrub Cup) Technique**

Baseline samples will be performed using sterile Stripping Suspending Fluid (SSF), and post-test material application samples will be performed using sterile Stripping Suspending Fluid with product neutralizers (SS+).

A sterile cylinder [REDACTED] will be held firmly onto the test site to be sampled. [REDACTED] of the appropriate sterile Stripping Suspending Fluid will be instilled into the cylinder, and the skin area inside the cylinder will be scrubbed in a circular motion with pressure for [REDACTED] with a sterile rubber policeman. The sampling fluid will be removed with a sterile pipette and transferred to a sterile test tube. A second [REDACTED] aliquot of the appropriate sterile Stripping Suspending Fluid will be instilled into the cylinder, and the skin area again scrubbed for [REDACTED] with a sterile rubber policeman. The second aliquot will then be pooled in the test tube with the first aliquot.

### **13.7 Diluting, Plating, and Counting**

Aliquots of the microorganism suspension ( $10^0$  dilution) will be serially diluted in Butterfield's Phosphate Buffer Solution with product neutralizers (PBW+) ([REDACTED] [REDACTED]). Serial dilution and plating will be completed within 30 minutes. Duplicate pour plates will be prepared from each of these dilutions with Tryptic Soy Agar with product neutralizers (TSA+) and incubated at  $30^{\circ}\text{C} \pm 2^{\circ}\text{C}$  for approximately 72 hours ( $\pm 4$  hours). Following incubation, plates may be refrigerated up to  $\sim 48$  hours prior to counting

Colonies will be manually counted and data recorded on appropriate data collection forms for each subject.

### **13.8 Blinding**

The study materials will not be blinded from the Investigator or other study staff performing the study material application or bacterial sample collections. In order to ensure "blinded" microbiologists, technicians who participate in plating samples and/or counting colonies on plates resulting from testing will not participate in the test product application or sample collection procedures. The blinding does not apply to baseline-screening samples.

### **13.9 Data Handling**

The estimated  $\log_{10}$  number of viable microorganisms per  $\text{cm}^2$  recovered from each sample site will be designated the "R-value."

To convert the volumetric measure of the sample into the number of colony-forming units per square centimeter ( $\text{cm}^2$ ), the following formula will be employed:

$$R = \log_{10} \left[ \frac{F \left( \frac{\sum c_i}{n} \right) 10^{-D}}{A} \right]$$

Where:

$R$  = the average colony-forming unit count in  $\log_{10}$  scale per  $\text{cm}^2$  of sampling surface

$F$  = total number of mL of stripping fluid added to the sampling cylinder; in this study,  $F =$  [REDACTED]

$\frac{\sum c_i}{n}$  = average of the duplicate colony counts used for each sample collected

$D$  = dilution factor of the plate counts

$A$  = inside area of the cylinder in  $\text{cm}^2$ ; in this study,  $A =$  [REDACTED]

**NOTE:** The reason that a  $\log_{10}$  transformation will be performed on the collected data is to obtain a linear scale. A linear scale, more appropriately a  $\log_{10}$  linear scale, is a basic requirement of the statistical models used in this study.

If colonies on one of the plates is uncountable, the count from the remaining plate will be used.

Colony counts of 0 will be set to 0.5 for further calculation purposes. The average for duplicate plates each containing 0 CFU's would result in an average of 0.5 CFU's further used for calculating the R Value.

Data collected from subjects with low or high test-day baseline counts on an anatomical test site ( $< 3.0 /> 5.5 \log_{10}$  CFU/ $\text{cm}^2$  from the skin of the abdomen, or  $< 5.0 /> 7.5 \log_{10}$  CFU/ $\text{cm}^2$  on the skin on the groin) will not be used in the Efficacy Analyses (Section 16.2). This is a common occurrence in clinical-simulation studies. Hence, more subjects will be enrolled and tested to account for test-day baseline failures.

## 14.0 DATA RECORDING

The raw data from sampling of all sites evaluated on a subject will be recorded on data collection forms.

## 15.0 ASSESSMENT OF SAFETY

### 15.1 Safety Assessments

The subject's safety will be monitored by evaluations of reactions observed on the skin of the test sites and any adverse reactions. Adverse reactions will be fully documented, reported as an Adverse Event, and followed to resolution.

## 15.2 Evaluation of Skin Reactions

The skin at each site will be evaluated visually for irritation per a scoring matrix (below) immediately before screening-baseline, baseline, and post-treatment samples are taken from each site. A subject will be dismissed from the study if skin irritation scores of 1 are observed on the test sites prior to screening-baseline or treatment day baseline sampling.

### SKIN IRRITATION SCORING SYSTEM

Condition	Rating	Description
Erythema	0	No reaction
	1	Mild and/or transient redness limited to sensitive area
	2	Moderate redness persisting over much of the product-exposed area
	3 *	Severe redness extending over most or all of the product-exposed area
Edema	0	No reaction
	1	Mild and/or transient swelling limited to sensitive area
	2	Moderate swelling persisting over much of the product-exposed area
	3 *	Severe swelling extending over most or all of the product-exposed area
Rash	0	No reaction
	1	Mild and/or transient rash limited to sensitive area
	2	Moderate rash persisting over much of the product-exposed area
	3 *	Severe rash extending over most or all of the product-exposed area
Dryness	0	No reaction
	1	Mild and/or transient dryness limited to sensitive area
	2	Moderate dryness persisting over much of the product-exposed area
	3 *	Severe dryness extending over most or all of the product-exposed area

\* = A score of 3 in one or more of the conditions evaluated represents significant irritation and qualifies as an Adverse Event.

## 15.3 Adverse Events

Adverse Events will be captured for all subjects from the time screening baseline samples are taken to the time of discharge from the study. Adverse Events will be categorized in relationship to a test material that was applied to the specific skin site. Emergency treatment is available onsite in the laboratory facility, and medical facilities/personnel are in close proximity.

In the event that either the Principal Investigator or the Sponsor determines that continuation of the study poses a hazardous risk of serious injury or death to the subjects, the study will be stopped.

A Photograph and Video Release Form ( [REDACTED] may be used (if subject agrees) in the even that an Adverse Event occurs for which the Principal Investigator is not onsite to observe [REDACTED]

[REDACTED]. This form will only be used with subject approval, and is not a requirement for participation in the study.

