## 7.6 Study Flow Chart

Procedure	Day			
	-14 or more	-3 or more	0	3 or more (Treatment Day)
Informed Consent Obtained	X			
Product-Restriction Period	X	X	X	X
Inclusion/Exclusion Criteria including Medical History Reviewed	X	X	X	X
Visual Skin Assessment		X		
Clipping Hair From Test sites		X		
Visual Evaluation of Skin Reaction			X	
Baseline Screening			X	
Pregnancy Test Administered (Females Only)				X
Visual Evaluation of Skin Reaction				X
Test-Day Baseline Sample				X
Product Application				X
30-Second Post-Product Application Visual Evaluation of Skin Reaction				X
30-Second Post-Product Application Sample				X
10-Minute Post-Product Application Visual Evaluation of Skin Reaction				X
10-Minute Post-Product Application Sample				X
Sample Sites Bandaged				X
6-Hour Post-Product Application Visual Evaluation of Skin Reaction				X
6-Hour Post-Product Application Sample				X
Test Materials cleaned from test sites				X

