### **13.2 Product Restriction Period**

The 14-day period prior to the baseline-screening portion of the study will be designated the "product restriction" period. During this time, subjects will avoid the use of medicated soaps, lotions, shampoos, deodorants, etc., as well as skin contact with solvents, acids, and bases. Subjects will also avoid sunbathing, using UV tanning beds or bathing in biocide-treated (e.g., chlorinated) pools and/or hot tubs. Subjects will be provided a kit containing products that they will be instructed to use exclusively for personal hygiene during the course of the study.

Subjects must not remove hair from the anatomical sites to be treated from the beginning of the product restriction period until after the testing has been completed. The subjects will be instructed not to bathe or shower for at least 72 hours prior to the baseline-screening sampling or the day of skin-treatment. This regimen will allow for the stabilization of the normal microbial flora of the skin.

During the latter portion of the product-restriction period (at least 72 hours prior to the test period), the subjects will be examined physically to ensure that there is no evidence of injury, dermatosis, or dermatitis present at the sampling sites, and hair on sampling sites will be clipped, if needed, to ensure that bandages used in testing will remain secure to the test sites (reference Appendix 2).

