#### **13.4 Baseline-Screening Sampling**

Baseline-screening samples will be taken on the day following the product restriction period. Subjects will not shower within a minimum of 72 hours prior to being sampled. Subjects will don a disposable undergarment prior to sampling, will be examined physically to ensure that there is no evidence of injury, dermatosis, or dermatitis present at the sampling sites (Section 15.2). A subject will be dismissed from the study if skin irritation scores of 1 or greater are observed on the test sites. If the subject continues to meet the study criteria, they will be sampled at the center of the test areas on the skin of the inguen and abdomen (Appendix 2) according to the Cylinder Sampling (Scrub Cup) Technique (Section 13.6).

There will be a minimum of 72 hours between the time the screening period ends and the experimental period begins. Based upon adequate screening microbial counts, subjects will be eligible to continue in the study.

Baseline criteria for qualification for the test period are  $3.0 \log_{10} \text{CFU}/\text{cm}^2$  from the skin of the abdomen, and  $5.0 \log_{10} \text{CFU}/\text{cm}^2$  on the skin on the groin. Subjects may qualify and be admitted into testing for both anatomical sites or one if the sample size minimums have been met for an anatomical region. If more subjects qualify (pass screening baseline) than can be tested in a group, or if they have a schedule conflict (or cannot test for another reason that does not affect their eligibility to test in the study), those subjects that qualify may be moved to a future group for testing the following week without having to re-qualify (clip or go through screening baseline again). If subjects that qualify need to move to a future group later than the following week, the subjects will be required to re-qualify (clip and go through screening baseline). Subjects who do not

qualify may be allowed to be screened again at the discretion of the Principal Investigator.

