### **15.3.1 Definitions**

#### **15.3.1.1 Adverse Event/Experience**

An Adverse Event/Experience is any unexpected or undesirable experience occurring to a subject during a study, which may or may not be related to a test material. All adverse event/experiences will be recorded and reported using Adverse Event documents according to the Standard Operating Procedures of the testing facility.

All Adverse Events, regardless of severity or the cause/effect relationship, are to be recorded. The severity of the effect will be noted as "Mild," "Moderate," or "Severe" according the following definitions:

Mild	Awareness of sign(s) or symptom(s), but easily tolerated.
Moderate	Discomfort to a degree as to cause interference with normal daily life activities and /or requiring medication.
Severe	Incapacity with inability to work or do usual daily life activities and requiring medical attention/intervention.

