### CHANGE(S):

In Section 13.3 on Page 19 of the Protocol, for the Left/Right Balance, the statement "The application will be randomized so that each treatment is used on an equal number of left and right sides of the body with the exception of replacement subjects." will be changed to, "The application will be randomized so that each treatment is used on an equal number of left and right sides of the body."

On page 2 of Appendix 1, the procedure for ZuraPrep™ Vehicle (Negative Control) [REDACTED]

[REDACTED] This will be changed to: [REDACTED]

In Section 15.4 (Anticipated Reactions), Page 27 of the Protocol, and on Page 8 of the Informed Consent Form as well as Page 7 of the Informed Consent Form - Neutralization Assay, in the Risks sections, folliculitis will be added as an anticipated reaction from clipping. For the Informed Consent Form, and new version of the Form will be created (Version 02) and approved by the GIRB. Clipping has already occurred for the neutralization, therefore, a subject letter will be signed by subjects who clipped in the neutralization – the letter will be approved by the GIRB. See attached letter for neutralization subjects, and version 02 of the Informed Consent Form.

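### Adverse event capture opens at the Day 0 screening sample, so reactions to study clipping that arise before that sample fall outside the window

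*Combined protocol and SAP*

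**What the plan says.** **Capture window.** Section 15.3: "Adverse Events will be captured for all subjects from the time screening baseline samples are taken to the time of discharge from the study".

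**Clipping.** Section 13.2 says that "hair on sampling sites will be clipped, if needed", and times this "During the latter portion of the product-restriction period". The flow chart in Section 7.6 has a row "Clipping Hair From Test sites", marked in the column for Day -3 or earlier. Consent is marked at Day -14 or earlier.

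**Screening sample.** Section 13.4: "Baseline-screening samples will be taken on the day following the product restriction period". The flow chart places it on Day 0.

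**Anticipated reaction.** The amendment that changes Section 15.4 states that "folliculitis will be added as an anticipated reaction from clipping". It also changes the consent forms and provides a letter for neutralization subjects who had already been clipped. None of the amendments in the document changes the start of adverse event capture.

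**Recording rule.** Section 15.3.1.1: "All Adverse Events, regardless of severity or the cause/effect relationship, are to be recorded". The definition there covers events during a study, whether or not related to a test material, and gives no start time. Section 15.3.3 requires the sponsor and the IRB to be told of all adverse events.

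**The concern.** Clipping is a procedure that the study carries out on consented subjects, and the sponsor thought its main risk worth adding to the consent form. The reporting window was not adjusted to match. Some harm from a study procedure can therefore go unrecorded as an adverse event and so not reach the sponsor or the IRB by that route. The subjects most likely to be missed include those whose skin reacted visibly enough for them to be dismissed at screening.

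What is at stake is the completeness of procedure-related safety reporting. The efficacy conclusion does not depend on it.

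**Working it through.** No statistical formula applies. The check is a timeline, followed by a sorting of cases.

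**Order of events.** Section 13.2 places clipping inside the product-restriction period. Section 13.4 places the screening sample on the day after that period ends. So the first clipping always comes before the sample that opens the window. This follows from the text alone.

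**Length of the gap.** In flow-chart days:

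- clipping to start of capture: 0 − (−3) = at least 3 days, nominally 3 × 24 = 72 hours;
- consent to start of capture: 0 − (−14) = at least 14 days.

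The first figure is nominal. Section 13.2 does give a lead of "at least 72 hours prior to the test period", but Section 13.4 uses the same term for the phase that subjects qualify for by their screening counts. The 72 hours may therefore be counted to treatment rather than to screening. The lead over screening rests on the flow-chart column, and in clock hours it could be slightly under 72.

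**Which clipping reactions are captured?**

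| Course of the reaction | In the Section 15.3 window? | Reason |
|---|---|---|
| Starts after clipping, resolves before Day 0 | No | Over before the sample is taken |
| Scored 1 or more on a test site at the Day 0 check | No | Sections 13.4 and 15.2: skin is scored just before sampling and the subject is dismissed, so the opening sample is not taken |
| First appears after the Day 0 sample | Yes | Window is open |
| Follows re-clipping of a subject already sampled who must re-qualify (Section 13.4 as amended 03/30/2017) | Yes | Window opened at the earlier sample |

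**Do other sections fill the gap?**

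- Section 15.3.1.2 grades causality only against a test material.
- Section 16.3 treats treated subjects as evaluable for safety, and limits any summary tables to subjects who enter the treatment period. A subject dismissed before treatment would not be in those tables.
- Sections 21.1 and 21.4 provide for progress notes and a disposition log. These are source records and not adverse event reports.

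**Effect of the change.** Starting capture at clipping reduces the uncovered time after clipping from at least 3 days to 0. Starting at consent would cover at least 14 days before screening.

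**Related gap.** Neutralization subjects are also clipped where needed (Appendix 3, Section 8.2), but their procedures describe no screening-baseline sample. Section 15.3 therefore gives them no defined start of capture.

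**The case against.** The strongest reply is that the gap is narrow and partly covered. Its parts are taken in turn.

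- **Not every clipping reaction is lost.** A reader might infer that all the anticipated clipping reactions fall outside the window. They do not, as the last two rows of the table show. This stands.
- **No count can be given.** A reader might infer that more than the 352 subjects needed to complete are affected, or that harm is under-reported for every clipped subject. Clipping is done only if needed, and neither the number clipped nor any reaction rate is stated. Harm goes unrecorded only where an event occurs in the gap. This stands.
- **The two rules can be read together.** Section 15.3.1.1 says what an adverse event is and Section 15.3 says when capture runs. Section 15.3.1.1 also defers to facility procedures that are not in the document. So this is not a flat contradiction. The plan still leaves staff to decide whether a consented, clipped subject is already in the study for recording purposes.
- **Serious events have their own wording.** A reader might infer that a serious event before Day 0 would go unreported. Section 15.3.3 requires immediate reporting of serious or unexpected events during the study, and review of unanticipated problems and deaths, without repeating the screening-sample start. The documents do not support the stronger inference.
- **Records would exist.** Criteria are reviewed at each visit, skin is examined at screening, and disqualified subjects are logged. That is correct, and it makes later recovery possible. It does not put the event into adverse event reporting.
- **Nothing in the document requires capture from consent.** This is accepted. The change rests on clipping being a study procedure with a named risk, so capture from clipping is enough.

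**Conclusion.** The gap holds in this limited form. As Section 15.3 is written, a clipping reaction that arises before the Day 0 sample is not captured if it resolves by then or leads to dismissal at the skin check. The uncovered time is nominally at least 3 days per clipped subject, taken from the flow chart. The number of events missed cannot be estimated from the document.

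Clipping comes before randomization and product application, so a reader should not infer any bias. Responder rates, log reductions and the safety comparison between products are unaffected. The consequence is possible under-recording of harm from a study procedure.

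The conclusion assumes that staff apply Section 15.3 literally and that no facility procedure outside the document starts capture earlier.

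**What to change.** 1. Amend Section 15.3 so that adverse event capture starts no later than the first study procedure on the skin, which is clipping. Give neutralization subjects a defined start in the same edit.
2. Reconcile Section 15.3 with Sections 15.3.1.1 and 15.3.3 and with the amended Section 15.4, so that all four use the same start.
3. List events before product application separately from treatment-emergent events.

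The cost is protocol wording, a few more adverse event forms and one extra listing. No visit is added, because subjects are already examined at clipping and again at screening.

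The amendment dated 08/29/2017 was issued after testing had finished, so new wording cannot recover unrecorded events in this study. What can still be done is to state the capture window as a limitation in the final report and to list pre-Day-0 skin reactions and dismissals from the source records and the disposition log.
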